The proposed observational study will evaluate the relationship between measures of psychopathology, disordered eating, and impulsivity, (each assessed preoperatively and in the early postoperative period) and changes in weight and psychosocial status in the first two years after bariatric surgery. Secondary outcomes of prevalence and control of T2D and hypertension, health services utilization, and adherence to antidiabetes and antihypertensive medication will also be assessed. All participants will complete assessments at baseline (before surgery) and at 6, 12, and 24 months follow-up. Secondary aims will examine psychopathology, disordered eating, impulsivity, as well as weight loss, in relation to changes in eating behavior, physical activity, psychosocial status, and substance use in the first two years after bariatric surgery. The study has one specific aim and two secondary aims. Specific Aim 1: To determine the relationship between psychopathology, disordered eating, and impulsivity assessed preoperatively and changes in body weight over the first two years following bariatric surgery. We will determine which individual measures falling under these constructs are important in predicting the relative success of bariatric surgery. We will also examine the relationship of changes in the individual measures (from baseline to 6-months after surgery) on subsequent weight loss. (The study is powered on this aim.) We predict that individual measures of psychopathology, disordered eating, and impulsivity will predict smaller weight losses two years postoperatively. We also predict that smaller changes in measures of impulsivity, psychopathology, and disordered eating within the first 6 postoperative months will be associated with smaller weight losses at postoperative month 24. Secondary Aim 1: To examine the correlation structure among our individual measures, and subsequently will generate and confirm composite measures for the three constructs. Composite measures of psychopathology, disordered eating, and impulsivity will predict smaller weight losses two years postoperatively. We also will estimate the proportion of variance in weight loss accounted for by each composite measure. We predict that confirmatory factor analysis will confirm that our individual measures represent three constructs of psychopathology, disordered eating, and impulsivity. Higher values of these composite measures will in turn predict smaller weight losses at postoperative month 24. Secondary Aim 2: To assess the relationship between baseline measures of interest and postoperative changes in caloric and macronutrient intake, eating behavior, physical activity, and psychosocial status. We predict that participants with greater psychopathology, disordered eating, and impulsivity will report greater caloric intake, less favorable changes in macronutrient intake and eating behavior, participate in less physical activity and report more symptoms of psychosocial distress.

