
The following documents are currently attached to this item:

There are no documents attached for this item.

Deception

Does your project use deception? No

Analysis Plan

Analysis will be conducted using Stata 13.0 (Stata Corporation, College Station, TX). After the completion of quality assurance procedures, descriptive statistics will be summarized for all patients by predictor group (dichotomized). Data screening: Prior to performing analyses, standard data screening/ cleaning procedures will be applied. These procedures will: screen the data for data-entry errors; check for outliers; assess the extent and pattern of missing data; create all summary scores needed for analysis; and check that appropriate assumptions of normality are met. In all analyses, the assumptions underlying the application of all the statistical methods that are used will be examined, principally through the use of standardized residuals, influence diagnostics, and graphical displays. Image processing will include image quality assessment procedures that examine global and region of interest (ROI) based raw and processed temporal signal-to-noise ratio, absolute and relative motion, and signal spike count. Potential outliers will be identified in the cumulative sample by examining quality assessment measures and flagging for further investigation subjects greater than two standard deviations from the mean on any one measure (i.e., behavioral performance, image distortion and artifact, general linear model fit). The purpose of this evaluation is to determine whether the time series is likely valid, and, if so, it will remain. Otherwise it will be corrected, if feasible, or removed from the analysis. The final sample will be examined in a similar fashion to determine whether any subjects warrant data cleaning or require exclusion from the final statistical analysis. Analysis of repeated measures: Our four-session within-subject design will generate multiple outcome measures that belong to the Gaussian family, and we will therefore use standard repeated-measures analysis of variance (ANOVA). Imaging outcomes (perfusion and BOLD) will be modeled using standard voxel-based image analysis techniques (described below) that incorporate random effects. Other outcomes (weight loss, ratings) will be modeled using a linear mixed-effects models framework, using using Stata 13.0 (Stata Corporation, College Station, TX). We could use a population averaged approach such as generalized estimating equations. However, the mixed model approach will provide the flexibility to allow for different error variances for different sessions if necessary. Voxel-based image analysis has limited flexibility, particularly when adding multiple covariates and interaction. When needed, summary values (e.g., mean rCBF, mean BOLD% signal change) extracted from ROIs will be modeled in STATAs mixed-models framework. These models can be extended to include additional explanatory variables (e.g., weight change, heart rate, respirations, age). Primary Aim 1 We will take a mixed models approach. The main interest in this study is the Group x Time interaction, where Group will be a between-subjects factor and Time will be a categorical within-subjects factor. This can be interpreted as population averages (GEE fitting method). Hypothesis 1: We will fit a 2 (Group: Dichotomized Baseline Measures, Low, High) x 3 (Time: change from baseline to month 6, 12 and 24) mixed-effects model for change in weight. Hypothesis 2: We will fit a 2 (Group: Dichotomized difference scores, 6 Month minus Baseline, Low, High) x 2 (Time: change from baseline to months 12 and 24) mixedeffects model for change in weight. In addition, the mixed effects models will include adjustments for surgical procedure, gender, and time since surgery. We recognize that the change in weight could also be associated with effects of several pertinent patient characteristics. To this end, we will consider additional covariates (e.g. sociodemographic variables, comorbidities, medication use, tobacco use, and initial weight). For both hypotheses, we will explore the continuous version of our predictor variables, where in place of Group, we use the real values of the predictor. This yields a difference of slopes with respect to predictor value across time points. Secondary Aim 1 We will use confirmatory factor analysis to verify our expected natural groupings of individual measures into composite measures. We will specify 3 factors and use Varimax rotation. We will assemble composite scores for each of our constructs by summing the standardized score values. We will then standardize the composite score and outcome (change in weight at 24 months). We will estimate the partial correlations (direct and indirect) among individual measures, composites, and outcome in a path analysis as suggested by Figure 1 to estimate the fraction of variance in outcome accounted for by each of the constructs. Secondary Aim 2 The outcomes will consist of (continuous) changes in behavior from baseline. We will use correlation to examine the relationship of baseline impulsivity measures to changes at 6, 12 and 24 months. The exception is changes in diet composition. In this analysis, we will use multivariate regression methods,

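### Aim 1 names the Group x Time interaction on weight change from baseline as its main interest; that term tests whether the Low-High gap varies between postoperative visits, not whether there is a gap at month 24

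*Combined protocol and SAP*

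**What the plan says.** In the Combined protocol and SAP, Analysis Plan, Primary Aim 1, Group is between subjects (Low or High on a dichotomised predictor), Time is categorical within subjects, and "The main interest in this study is the Group x Time interaction".

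- Hypothesis 1 uses baseline predictors in a two-group model "x 3 (Time: change from baseline to month 6, 12 and 24) mixed-effects model for change in weight".
- Hypothesis 2 uses the 6-month change in each predictor in a two-group model "x 2 (Time: change from baseline to months 12 and 24) mixedeffects model for change in weight".
- The exploratory continuous version replaces Group with the predictor value: "This yields a difference of slopes with respect to predictor value across time points".

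The predictions are in Overall objectives, Specific Aim 1. The first is that "individual measures of psychopathology, disordered eating, and impulsivity will predict smaller weight losses two years postoperatively". The second is that smaller early changes in those measures "will be associated with smaller weight losses at postoperative month 24". The Weight paragraph under Procedures repeats the month-24 prediction. Specific Aim 1 itself is worded more broadly, as "changes in body weight over the first two years following bariatric surgery".

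Month-24 weight change is the stated outcome of one analysis only, the Secondary Aim 1 path analysis: "We will then standardize the composite score and outcome (change in weight at 24 months".

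**The concern.** Subtracting baseline and then dropping it as a Time level changes what the interaction means. The between-group difference in weight loss becomes the Group effect at each visit, and the interaction holds only the variation in that difference from visit to visit. The Aim 1 section names neither a Group effect nor a month-24 contrast, and the continuous version is also described as a comparison across visits.

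If inference rests on the named term, it can mislead in two ways. Participants high on a predictor may lose less weight by month 6 and stay behind; the prediction is then true, but the named test has no power beyond alpha. Or an early difference may disappear by month 24; the prediction is then false, but the named test is likely to be significant. Choosing the month-24 contrast after seeing the results would be the kind of discretion a plan is meant to remove.

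**Working it through.** **1. What the interaction tests.** Let g6, g12 and g24 be the Low-minus-High differences in mean weight lost from baseline. Write the Hypothesis 1 model with month 6 as reference: Group coefficient b, interaction coefficients c12 and c24. Then

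- g6 = b, g12 = b + c12, g24 = b + c24.
- Interaction null (2 df): c12 = c24 = 0, that is, g6 = g12 = g24.
- Month-24 prediction: g24 = b + c24 differs from 0.

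For Hypothesis 2, with month 12 as reference, the interaction null (1 df) is g12 = g24. Neither null is g24 = 0. With a constant gap the interaction's noncentrality is exactly 0, so the no-interaction null is rejected at alpha whatever the N, SD or correlation.

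By contrast, if weight itself were the outcome and baseline a Time level, the month-24 Group x Time coefficient would equal g24.

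**2. Inputs for the size.** The text available gives 300 completed baselines but no SD, correlation or effect size, so there is no power figure to reproduce. Assumed: 240 analysed in equal groups of 120; SD of change 6-8, 8-9 and 10 points at months 6, 12 and 24; common correlation 0.6 to 0.9; two-sided alpha 0.05.

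**3. Month-24 contrast.** Variance = 10² × (2/120) = 1.667. For a 4-point gap the noncentrality is 4²/1.667 = 9.6, so power is 87%. The gaps at earlier visits do not enter.

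**4. Hypothesis 2 interaction, one worked case.** With SDs 9 and 10 and correlation 0.7, the within-person variance is 81 + 100 − 2 × 0.7 × 90 = 55. The variance of g24 − g12 is 55 × 2/120 = 0.917.

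- Gap 3/4: 1²/0.917 = 1.09, power 18%.
- Gap 2/0: 2²/0.917 = 4.36, power 55%.

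**5. Hypothesis 1 interaction, one worked case.** The noncentrality is d′W⁻¹d, where d = (g12 − g6, g24 − g6) and W is its covariance matrix. With SDs 8/9/10 and correlation 0.7, W = (2/120) × [44.2, 20.6; 20.6, 52].

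- Gap 2/3/4: d = (1, 2), and 60 × (52 − 82.4 + 176.8)/1874.04 = 4.69, power 48%.
- Gap 4/2/0: d = (−2, −4), four times as large, 18.75, power 98%.

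**6. Full range over the assumed SDs and correlations.**

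| Hypothesis | Gap by visit | Interaction | Month-24 contrast |
|---|---|---|---|
| 1 | 4/4/4 | 5% | 87% |
| 1 | 3/3.5/4 | 12-34% | 87% |
| 1 | 2/3/4 | 38-90% | 87% |
| 1 | 1/2/4 | 72% to over 99% | 87% |
| 1 | 1/3/4 | 76% to over 99% | 87% |
| 1 | 0/2/4 | 93% to over 99% | 87% |
| 1 | 4/2/0 | 93% to over 99% | 5% |
| 2 | 4/4 | 5% | 87% |
| 2 | 3.5/4 | 7-14% | 87% |
| 2 | 3/4 | 15-43% | 87% |
| 2 | 2/0 | 44-94% | 5% |

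For 2/3/4 the interaction reaches 38-50% at correlation 0.6-0.7, 59-65% at 0.8 and 75-90% at 0.9.

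**7. Checks.** Simulation (complete data, unstructured covariance estimated, 4,000 replicates per scenario) gave 4.7-5.4% for the interaction and 86-87% for the contrast under 4/4/4, and 93-100% and 4.5-5.2% under 4/2/0. With other assumptions (150 per group, SD 10 throughout, correlation 0.7), the constant gap gives 5% against 93%, and 2/3/4 gives 50% against 93%.

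**The case against.** The algebra is hard to dispute; the case against concerns intent, mitigation and scale.

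- **Intent.** The plan mentions a four-session design and labels the Time factor itself as change from baseline. If weight was meant to be the outcome with baseline as a Time level, the month-24 interaction coefficient would be the right term. But both hypotheses say the model is for change in weight and give only postoperative levels. This reading needs a clarification before it can be relied on.
- **Main interest is not a decision rule.** The fitted model can give the gap at each visit, and routine reporting may show it. True: the analysis is usable. What is missing is the designation.
- **Mitigation.** The Secondary Aim 1 path analysis uses month-24 weight change and includes individual measures as well as composites. That is a real partial remedy, but it belongs to a secondary aim and does not cover the 6-month change scores of Hypothesis 2.
- **Trajectory is a legitimate target.** Specific Aim 1 covers the whole two years, and the Background describes regain after year 1, which makes a widening gap plausible. The table shows the interaction matching or beating the contrast when widening is substantial. This justifies keeping the interaction, but it does not make it a test of the month-24 predictions.
- **Assumed magnitudes.** The 87% needs equal groups. No cut-point is given and some predictors are presence/absence diagnoses. With a 20/80 split, month-24 power falls to about 70%, and with 5/95 to about 27%. This stands: 87% will not apply to every predictor. The alpha-level result under a constant gap needs none of these assumptions.

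**Conclusion.** The concern holds. As written, the term named as the main interest of Aim 1 does not test the Aim 1 predictions, and it can mislead in either direction. That much is algebra and depends on no assumed figure.

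How much power is lost or gained depends on the assumptions listed above and on the shape of the gap over time. The interaction performs worst when the gap is steady or widens slowly, and it is comparable or better when the gap emerges late. The harm arises if inference rests on the named term. The plan names no other for the aim on which it says the study is powered, so this should be corrected before the Aim 1 analysis.

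**What to change.** Keep the mixed models as specified. State that the primary test for Hypothesis 1 and Hypothesis 2 is the model-based Low-High difference in weight change at month 24 (b + c24 in the notation above). For the continuous version, state that it is the month-24 slope per SD of the predictor. Report the Group x Time interaction and the earlier-visit contrasts as secondary descriptions of trajectory.

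If the intended model was weight as outcome with baseline as a Time level, say so, correct the description of the outcome and Time levels, and name the month-24 Group x Time coefficient as the primary test.

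The cost is one or two sentences in the Analysis Plan, with no new data and no change of model. The price is some loss of power relative to the interaction if the gap emerges late or widens substantially.

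### Both Aim 1 primary models rest on a Low/High split with no stated cut-point, while the model with actual predictor values is only exploratory: efficiency is forgone and the cut is left open

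*Combined protocol and SAP*

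**What the plan says.** Under Analysis Plan, Primary Aim 1, the test of interest is stated outright: "The main interest in this study is the Group x Time interaction". For Hypothesis 1, Group comes from "2 (Group: Dichotomized Baseline Measures, Low, High) x 3" time points (change to months 6, 12 and 24). For Hypothesis 2 it comes from "Group: Dichotomized difference scores, 6 Month minus Baseline, Low, High", with two time points (months 12 and 24). The same section adds: "For both hypotheses, we will explore the continuous version of our predictor variables", meaning that "in place of Group, we use the real values of the predictor".

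The supplied text names no median, threshold or other rule for Low and High, and gives no reason for splitting. The descriptive tables use the same undefined groups.

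Data screening says the team will "check that appropriate assumptions of normality are met". It also describes flagging values more than two standard deviations from the mean, then keeping, correcting or removing them. It does not say on what scale a skewed predictor enters a model.

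Under Objectives, Specific Aim 1, the protocol states: "The study is powered on this aim". Study Instruments and Procedures (Eating Behavior) both say that EDE-BSV results will enter the analyses as a continuous variable.

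**The concern.** Many Aim 1 measures are graded: stop-signal reaction time, Stroop interference, the discount rate k, BDI-II, the Eating Inventory factors and the night-eating score. Splitting such a score treats everyone on one side of the cut as alike. If the association is roughly linear, that discards information in the main test of the aim the study says it is powered on.

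The missing cut is a separate matter. The power of the split model depends on where the cut falls. If the cut can be settled after the data are seen, the nominal 5% error rate of the primary test is no longer guaranteed. For Hypothesis 2, a published threshold for a baseline score would not supply a cut for a difference score.

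EDE-BSV adds a smaller tension. A primary model built on dichotomized measures sits uneasily with the statement that this measure will be continuous.

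**Working it through.** **Inputs from the documents.** N = 300 completing baseline (Accrual); a two-level Group; three time points for Hypothesis 1 (interaction on 2 df) and two for Hypothesis 2 (1 df).

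**Assumed, because not given.** Two-sided alpha 0.05, 80% power as the reference, normal predictor, linear effect.

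**1. The plan's own figure.** The 300 cannot be reproduced, since no alpha, power, effect size, SD or dropout accompanies it. For scale only, a 150/150 split at one time point detects (1.960 + 0.842) x sqrt(2/150) = 0.32 SD with 80% power. That restates 300; it does not confirm it.

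**2. Information kept by a split.** With a share p below cut c, the fraction kept is phi(c)^2 / [p(1-p)], where phi is the normal density.
- 50/50: 0.3989^2 / 0.25 = 0.637 (that is, 2/pi, the best case); 300 x 0.637 = 191 effective participants
- 30/70: 0.3477^2 / 0.21 = 0.576
- 20/80: 0.2800^2 / 0.16 = 0.490

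**3. Power, from the noncentral chi-square.** For 80% power the noncentrality is 9.635 (2 df) or 7.849 (1 df).

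| Sized so that | Model | Hyp. 1 (2 df) | Hyp. 2 (1 df) |
|---|---|---|---|
| continuous has 80% | median split (noncentrality x 0.637 = 6.13; 5.00) | 59.4% | 60.8% |
| continuous has 80% | 20/80 split (x 0.490) | 48.0% | 50.0% |
| median split has 80% | continuous (noncentrality / 0.637 = 15.13; 12.33) | 94.6% | 94.0% |
| median split has 80% | 30/70 split | 75.6% | 75.9% |
| median split has 80% | 20/80 split | 68.2% | 69.1% |

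**4. Cut chosen after the data.** Simulation with no true effect, n = 300, 20,000 runs, smallest p-value kept, for one predictor:
- fixed median: 5.1% (2 df), 5.2% (1 df)
- best of 3 cuts (33rd, 50th, 67th percentile): 11.9%, 11.6%
- best of 7 cuts (20th to 80th percentile): 20.2%, 19.8%

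**5. Raw values are not always better than the split.** Suppose a predictor is lognormal with log-scale SD s and the effect is linear in its log. In large samples raw values keep s^2 / (exp(s^2) - 1): 1/1.718 = 0.58 at s = 1, falling below the median split's 0.637 once s exceeds 0.92. A simulation of the three-time interaction at n = 300 (4,000 runs) gave these powers:
- s = 1: log 80.0%, median split 59.9%, raw 57.1%
- s = 1.5: log 80.5%, median split 60.8%, raw 40.0%

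If instead the effect is linear in the raw value (s = 1), the log keeps 58% and the median split 27%. The log beats the split in both cases; raw values do not.

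**6. Binary measures.** At baseline, a 0/1 measure loses nothing when called Low/High. Its 6-month difference has three levels (-1, 0, +1), and two groups must merge two of them. The fraction of linear information kept is cov^2 / (variance of difference x variance of group). Assumed example with 15% / 80% / 5% at -1 / 0 / +1 (variance 0.20 - 0.10^2 = 0.19):
- -1 against the rest: 0.135^2 / (0.19 x 0.1275) = 75%
- +1 against the rest: 0.055^2 / (0.19 x 0.0475) = 34%

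With 10% / 80% / 10%, either cut keeps 56%.

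**The case against.** The strongest reply is that the continuous model is already planned, and that, taken literally with raw values, it can do worse than a median split for a skewed predictor such as k might be. This stands in part: step 5 confirms it, so exchanging the two analyses as written is not enough and the scale must be stated too. It does not defend an undefined split as the deciding test.

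Other points carry some weight. Procedures (Weight) words the prediction as higher against lower levels, which fits a two-group contrast; it still sets no cut, and a slope tests the same direction. A true threshold effect could favor a split at that threshold, but the supplied text argues for none. Secondary Aim 1 already relates standardized composites to 24-month weight change, so graded information is not ignored throughout. Log scales do not suit scores with many zeros; the Background reports current substance use below 2% in earlier surgical candidates, so alcohol and nicotine scores may well be of this kind.

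Two stronger readings are tempting. A reader might infer that the study is underpowered: the documents do not support this, because they give no power inputs and 300 may have been sized for two groups. A reader might also infer that the team means to choose cuts after seeing results: nothing in the text shows that, and the error rates in step 4 are worst cases. Two parts of the file are absent from the supplied text, so a cut or power calculation could stand there.

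**Conclusion.** The point holds as one of priority and specification. The main Aim 1 test uses an undefined Low/High split of graded measures, and the more informative form is only exploratory. Under normality and linearity the split keeps at most 64% of the information. Whether that appears as 80% power falling to 59-61%, or as 94-95% given up for 80%, depends on how 300 was sized, which is not stated. The size changes with the predictor's shape and the cut.

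The open cut is a weakness however the study was sized: power in the split model moves with it, and control of the false-positive rate rests on fixing it in advance. The point applies to graded measures in both hypotheses and, through the three-level difference, to binary measures in Hypothesis 2. It does not apply to baseline binary measures in Hypothesis 1. The EDE-BSV statement is an ambiguity about which analyses it covers rather than a proven contradiction. The change is worth making, since its cost is small and it bears on the primary aim.

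**What to change.** - For each graded measure, make the continuous predictor (per SD) x Time model primary in both hypotheses, on a scale written down before analysis: for example log k for the discount rate.
- For scores with many zeros, such as alcohol or nicotine measures, state a suitable coding, since the log is undefined at zero.
- Check linearity with a spline or quadratic term.
- Keep Low/High for descriptive tables and a supportive analysis, with the cut for each measure, and its source if a threshold is meant, fixed in advance.
- Leave baseline binary measures as they are in Hypothesis 1. In Hypothesis 2, state a coding of their three-level difference that does not merge levels arbitrarily.
- Say which analyses the continuous EDE-BSV statement refers to.

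The cost is a change of priority plus one line per measure on scale and cut; no new data or visits are needed. The small downside is that a slope per SD is less immediate to read than a two-group contrast. Showing predicted weight change at two stated predictor values beside it meets most of that.

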
Characteristics of the Study Population

Target population

Adults aged 18-65 years old who plan to undergo one of two bariatric surgeries, either Rous-en-Y Gastric Bypass (RYGB) or Laparoscopic Sleeve Gastrectomy (LSG) at the University of Pennsylvania Health System. Based on our previous studies of bariatric surgery patients, we expect that approximately 80% of participants will be women and 20% of participants will be ethnic minorities.

Subjects enrolled by Penn Researchers 300

Subjects enrolled by Collaborating Researchers

0

Accrual

Participants will be recruited from the Bariatric Surgery Programs at the Hospital of the University of Pennsylvania and Presbyterian Medical Center, all part of Penn Medicine. We will enroll participants until a total of 300 adults have completed baseline visits. We anticipate that we will need to consent a larger number of participants in order to meet this enrollment goal. Based on our previous studies of bariatric surgery patients, we expect that approximately 80% of participants will be women and 20% of participants will be ethnic minorities. [name], Director of the Bariatric Surgery Program, conducts approximately 300 bariatric surgery operations per year. Additional surgeons in the Bariatric Surgery Program (at the Hospital of the University of Pennsylvania, Presbyterian Medical Center, and Pennsylvania Hospital) operate on approximately 200 patients per year. In order to increase the diversity and size of our sample, participants will also be recruited from the Temple Health Bariatric Surgery Program. The patient flow at Temple Health is similar to that of the Penn Health System (described below). Participants will be approached by the Research team during their pre-operative testing and education process.

Key inclusion criteria

We seek to enroll a sample of patients that is representative of those who present for bariatric surgery. We have based our exclusion criteria for the study largely on the clinical criteria used for bariatric surgery as well as our previous studies with bariatric patients. Inclusion Criteria: Adults aged 18-65 years old 18 years of age or above BMI of 35-60 kg/m2 (or 35 kg/m2 in the presence of significant weight-related comorbidities, including established coronary artery disease, established peripheral arterial disease, symptomatic carotid artery disease, sleep apnea, metabolic syndrome, cardiomyopathy, hypertension, and debilitating joint pain).

Key exclusion criteria

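### Hypothesis 2 relates early change to later weight with no pre-specified term for the measure's own baseline, so the High-Low difference can be attenuated, cancelled or reversed

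*Combined protocol and SAP*

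**What the plan says.** The Analysis Plan (Primary Aim 1) tests two hypotheses in separate models of weight change. Hypothesis 1 uses the baseline value of each measure: "We will fit a 2 (Group: Dichotomized Baseline Measures, Low, High"), crossed with change to months 6, 12 and 24. Hypothesis 2 uses the early change: "We will fit a 2 (Group: Dichotomized difference scores, 6 Month minus Baseline, Low, High"), crossed with change to months 12 and 24. The plan names the Group x Time interaction as the main interest.

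For covariates, "the mixed effects models will include adjustments for surgical procedure, gender, and time since surgery". Beyond these, "we will consider additional covariates (e.g. sociodemographic variables, comorbidities, medication use, tobacco use, and initial weight"). That open list names the baseline of the outcome (initial weight) but not the baseline of the predictor. The exploratory continuous analysis only swaps in the undivided score: "For both hypotheses, we will explore the continuous version of our predictor variables, where in place of Group, we use the real values of the" (the quoted sentence breaks off here, one word before its end).

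The predicted directions are in Objectives, Specific Aim 1. For baseline: "We predict that individual measures of psychopathology, disordered eating, and impulsivity will predict smaller weight losses two years postoperatively". For early change: "smaller changes in measures of impulsivity, psychopathology, and disordered eating within the first 6 postoperative months will be associated with smaller weight losses", with month 24 as the time point. The sample is set under Accrual: "We will enroll participants until a total of 300 adults have completed baseline visits".

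**The concern.** Baseline enters the Hypothesis 2 predictor with a minus sign. A patient with a low starting score has little room to improve, while a patient with a high score can fall a long way, partly through regression to the mean. The less-improved (High difference) group is therefore enriched for low-baseline patients. Hypothesis 1 expects those patients to lose more weight; Hypothesis 2 expects the less-improved group to lose less. With no baseline term, the High-Low comparison cannot separate these two influences.

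At stake is how part of Specific Aim 1 is read. A real association with early change could look like nothing. An association carried only by baseline could look as if patients who improve less do better.

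**Working it through.** **Inputs.** The plan supplies the form of the predictor, the covariates and the predicted signs. It gives no correlation, SD or effect size for this point, so there is no figure to reproduce. The values below are assumptions.

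**Set-up.** X0 and X6 are one measure at baseline and 6 months (higher = worse), each with SD 1 and correlation r. Weight loss in SD units at one visit is Y = a·X0 + c·X6 + error. D = X6 − X0; High D means less improvement. Hypothesis 2 predicts a negative High-Low gap.

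**Step 1: coupling with baseline.** corr(X0, D) = −√((1−r)/2).
- r = 0.4: −√0.30 = −0.55
- r = 0.7: −√0.15 = −0.39

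**Step 2: what the unadjusted gap estimates.** cov(D, Y) = (1−r)(c−a) and SD(D) = √(2(1−r)). For a median split of a normal D, the gap is 4φ(0)·cov(D, Y)/SD(D), with φ(0) = 0.3989. This gives

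gap = 1.596 × (c−a) × √((1−r)/2).

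It depends only on the 6-month effect minus the baseline effect.

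**Step 3: baseline-adjusted gap.** Write q² = (1−r)/2. With X0 as a continuous covariate,

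gap = c × SD(D) × 0.3989(1−q²)/(0.25 − 0.1592q²).

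| r | Unadjusted, a=−0.2, c=0 | Unadjusted, a=c=−0.2 | Adjusted, a=c=−0.2 | Unadjusted, a=0, c=−0.2 |
|---|---|---|---|---|
| 0.4 | +0.175 | 0 | −0.303 | −0.175 |
| 0.5 | +0.160 | 0 | −0.285 | −0.160 |
| 0.6 | +0.143 | 0 | −0.262 | −0.143 |
| 0.7 | +0.124 | 0 | −0.232 | −0.124 |

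When only baseline matters (c = 0), the adjusted gap is zero. If percent weight loss had an SD of 10 points (assumed), the first column would be 1.24 to 1.75 points in the wrong direction.

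**Step 4: frequency in a trial of this size.** Simulation with 240 analysed of the 300 (assumed), r = 0.6, residual SD 1, median split, one time point, 1,500 replicates, two-sided 0.05:
- a = −0.3, c = 0: 33% of unadjusted tests are significant in the reversed direction; 3% after adjustment.
- a = c = −0.15: mean gap 0.00 unadjusted and −0.19 adjusted; 2% and 28% significant in the predicted direction.
- a = 0, c = −0.3: the sign is kept, but the mean gap is −0.21 unadjusted against −0.39 adjusted; 36% and 79% significant.

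**Step 5: Group x Time.** Step 2 applies separately at months 12 and 24. The baseline contribution to the change in gap between visits is −1.596 × (a24 − a12) × √((1−r)/2). It is zero when a24 = a12.

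**Step 6: unequal SDs.** In terms of change, the unadjusted slope on D is −(b2 − b1·w), where b1 = −(a+c) is the harm from baseline at given change, b2 = −c is the harm from less improvement at given baseline, s is the 6-month SD relative to baseline, and w = (1−rs)/(1+s²−2rs). At s = 1, w = 0.5. For r from 0.3 to 0.8, w is 0.61 to 1.19 when s is 0.7 to 0.85 (cancellation comes sooner) and 0.08 to 0.37 when s = 1.2 (later).

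**The case against.** **The main contrast is an interaction.** The gaps above are group differences at one visit. By Step 5, a baseline effect equal at months 12 and 24 drops out of Group x Time and distorts only the Group effect. This stands. The point still matters because Specific Aim 1 words its prediction as weight loss at month 24, which is a group difference at that visit.

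**Other effect patterns are harmless or milder.** With equal SDs, the sign is kept whenever the 6-month level matters more than baseline. With a = −0.1 and c = −0.2 the unadjusted gap is half the last column, −0.062 to −0.087. If weight loss depends on change alone (a = −c), the unadjusted slope is unbiased. Hypothesis 1 does not settle which case holds: it concerns the total baseline slope, a + c·r, which is negative even when a = 0 and c < 0. This also stands.

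**Adjustment can mislead too.** Suppose both scores are noisy readings of one stable trait, and only the trait affects weight. Then a = c, the unadjusted gap of zero is correct, and the adjusted gap of −0.23 to −0.30 SD reflects measurement error, not change. The documents do not say which model holds, so the adjusted result should not simply replace the current one.

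**The question shifts.** With continuous change plus baseline, the coefficient on change equals that of the 6-month level given baseline. Specific Aim 1 speaks of changes in the measures, so the conditional target must be stated.

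**Stronger readings that a reader might infer.**
- That small change largely means low baseline. The share of low-baseline patients in the less-improved half is 1/2 + arcsin(|corr|)/π, or 63% to 68% for correlations of −0.39 to −0.55, against 50% by chance. About a third do not fit.
- That every measure falls early. The Background ties only depressive symptoms to the first six months. It places the fall in anxiety in the first year, gives no month for disinhibition and hunger, and reports that substance use can rise.
- That the plan rules out baseline adjustment. The covariate list is illustrative, so adjustment is unspecified, not forbidden.

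**Conclusion.** The point holds as a risk, not a certainty. No pre-specified Hypothesis 2 model holds the measure's own baseline constant, and the difference score is negatively correlated with that baseline (−0.55 to −0.39 under the stated assumptions). The High-Low difference at months 12 and 24 can therefore be weakened, cancelled (zero when a = c) or reversed (+0.12 to +0.17 SD when only baseline matters at −0.2). A reader might conclude that Hypotheses 1 and 2 necessarily contradict each other, or that Hypothesis 2 will come out reversed. The documents do not support that: it depends on the relative effects of the two levels and on the SDs, none of which they give, and the interaction is distorted only if the baseline effect differs between months 12 and 24.

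These sizes rest on r of 0.4 to 0.7, equal SDs, illustrative coefficients and a median split of a normal difference. This is an inexpensive improvement that guards against a wrong-sign reading; it does not invalidate the aim.

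**What to change.** In the Analysis Plan, Primary Aim 1, pre-specify a second Hypothesis 2 model. It adds the continuous baseline value of the same measure and its interaction with Time, in both the dichotomized and continuous versions. Report it alongside the current unadjusted model.

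State that the added model estimates the association of 6-month change with later weight at a given baseline level, and that in the continuous version its coefficient is that of the 6-month level given baseline. State also that the two models are to be read together: a null unadjusted result with a non-null adjusted one is compatible either with a masked association or with measurement error around a stable trait.

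The cost is a few sentences and no new data, because the difference score already requires the baseline value. Precision falls. For continuous change the variance inflation is 1/(1−q²), or 1.18 to 1.43 for r from 0.7 down to 0.4. For the split it is 1/(1−2q²/π), or 1.11 to 1.24.
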